12.3. Populations for Analyses

Clearly identify and describe the analysis datasets (e.g., which participants will be included in each).

exercise plus placebo (EX+PLA) vs. exercise plus BCAA (EX+BCAA)

12.4. Statistical Analyses

Include analysis of primary efficacy endpoints, secondary endpoints, safety analyses, and any planned interim analyses

In collaboration with RC3 (Trial Design and Integrative Informatics Core), two separate independent sample t-tests will be used for each outcome measure: one to compare change before and after acute exercise (during the 400 m walk) between the two groups and one to compare change before and after chronic (8-week) exercise training between the two groups. This will determine the significance of our primary outcomes (fatigue and tryptophan metabolism) change over time. All statistical tests will be 2-sided and unadjusted for multiple comparisons. We are eschewing the mixed model analysis of variance (ANOVA) to account for the time effect. The repeated measures ANOVA would be testing more effects than we are exploring here, and the study is not powered for this advanced analysis.

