5.2. Overall Design Select all applicable												
	Randomization				Cluster Randomized							
	Group-Sequential				Adaptive Design							
	Parallel Design				Placebo-Controlled							
	Superiority				Equivalence				Non-inferiority			
Device		Pilot			Pivotal				Post-Approval			
Drug/Biologic		Phase 1		Phase 1/2		Phase 2		Phase 2/3		Phase 3		Phase 4
	Dose escalation		If yes, details →									
	Dose ranging		If yes, details →									
	Sub-studies		If yes, details →									
5.3. Other Design Details: Experimental Test by Phase: The experimental design of this study involves 5 phases, completed over 3-4 months. Phase 1 involves recruitment, screening, and enrollment. Phase 2 involves baseline testing. Volunteers then will be randomly assigned to exercise plus placebo (EX+PLA) vs. exercise plus BCAA (EX+BCAA) (Phase 3). Randomization will be 1:1 using a random number generator, assigning participants down the list in order of eligibility. Phase 4 consists of eight weeks of either 3x/week EX+PLA or EX+BCAA. After the intervention, subjects will undergo final research testing (Phase 5). All research testing and training will occur at the Barshop Institute. Intervention staff and participants will be blinded (double blinded) to supplement allocation. Participants will receive either a supplement or a placebo, both in powder form. Only study team member without direct participant interaction (i.e., statistician) will know supplement allocation. Refer to section 10.1 for further information on randomization and blinding.												

6. Study Population									

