Screening: Eligible volunteers will have the study explained and provide informed consent according to the guidelines of the UT Health San Antonio IRB. Participants will be asked to supply the name and contact information of their primary care provider during the consent/screening phase. An in-clinic evaluation consisting of medical history and physical exam (including EKG) will be conducted by a research clinician. Information on demographics and family medical history will be recorded. A fasting blood profile for lipids, liver, renal and hematological function will be drawn. We will draw approximately 30 ml of blood (about 2 tablespoons) during screening (*Phase 1*). Although we do not expect a problem with the collection of blood samples, should a problem arise, such as clotting or insufficient sample for analysis, we may draw additional blood, not exceeding 50 ml (10 teaspoons) throughout any study visit. Height and weight will be measured using a standard physician's scale. Seated blood pressures will be measured. Questionnaires to screen for depression and cognitive impairment will be administered to determine eligibility.

Enrollment: Participants will be enrolled if they provide informed consent and pass all required screening assessments.

Baseline Research Testing (Phase 2): Data for primary and secondary outcomes will be collected using standardized protocols and trained staff. All baseline testing will be conducted at the Barshop Institute over approximately 3-4 visits during approximately 2-4 week period. These tests are described in detail below.

Randomization (Phase 3): Assigned (1:1 randomization) to either EX+PLA or EX+BCAA. After randomization, vital signs and blood will be drawn before (following a 12 hour fast) and acutely (3-5 min) after completing a 400 m walk test. After the fasting blood draw, participants will receive (blinded) either ~7-10 g of BCAAs (100 mg/kg) or maltodextrin (depending upon group allocation) 30 min prior to beginning this test. Heart rate and ratings of perceived exertion will be collected throughout the 400 m walk test. Participants will be instructed to document their food intake on Food Record form during the 2 days before the 400 m walk test and to repeat this diet before the post intervention test.

Exercise + Placebo or Exercise + BCAA (Phase 4):

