Exercise: The 3x/wk for eight weeks exercise protocol is designed to provide a high-volume, moderate-intensity whole body training stimulus for all participants. The sessions will occur at the Barshop Institute and be led by an exercise physiologist.

Aerobic exercise training will start conservatively with a goal of 30 minutes total duration at 40-50% maximal heart rate reserve (HRR) determined according to the formula of Karvonen: Training HR = % (HRmax - HRrest) + HRrest. HRmax is defined as peak heart rate based during a peak Cardiopulmonary Exercise Test (described above). Treadmill exercise is advanced weekly, as tolerated to an intensity of 75-85% HRR for 30 minutes. Additionally, participants will perform resistance exercise consisting of 15 repetitions for two sets and to exhaustion on the third set for five major muscle groups: chest press, knee extension, leg curl, row, and bicep curl. Resistance is gradually increased to account for strength gains when participants are able to complete 20 repetitions on the third set.

BCAA or Placebo: Participants will be randomized 1:1 to eight weeks of BCAA or maltodextrin (PLA) supplementation. Participants will be instructed to consume either ~7-10 g of BCAAs (100 mg/kg body weight) (2:1:1 leucine:isoleucine:valine) or PLA powder. In the Barshop Institute pharmacy, intervention blinded study staff wearing hair net, gloves and a facemask will weigh the required participant dose via nutrition food scale and place the daily dose in disposable condiment containers and labeled with dates for daily intake. Powders will be distributed in a double-blind fashion, identical in color, and dissolved in water or a non-calorie drink of their choice (i.e., Crystal Light). On non-exercise days, participants will be instructed to take the supplement between 9 - 10 am each morning and to log each intake in a provided spreadsheet. Powders to be consumed on non-exercise days will be pre-packaged containers and provided to participants on a weekly basis. On exercise days, the supplement will be consumed immediately after finishing exercise training. Supplement containers also will be returned every two weeks to track compliance. Assessment of side effects will occur at every exercise session.

Post Intervention Testing (Phase 5): Participants will repeat tests outlined in Phase 2 and the submaximal exercise test outlined in Phase 3.

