8.4. Laboratory Tests

- a) **Laboratory Test:** We will collect plasma, serum, and whole blood for assessment of heart disease risk factors, complete blood count (CBC), comprehensive metabolic panel with liver function tests, lipid profile (e.g., triglycerides, lipoproteins, free fatty acids), glucose, insulin, systemic and cellular inflammation biomarkers, oxidative stress, antioxidant capacity, obesity-related factors (e.g., leptin and adiponectin), and amino acid metabolism.
- b) **Skeletal Muscle Biopsies and Analysis:** Vastus lateralis muscle biopsies will be obtained with a Bergstrom needle with local anesthesia by a credentialed clinician following a 12 hour fast. Muscle tissue will quantitate local inflammation and tryptophan metabolism markers. The samples will be placed in OCT for fiber typing or immediately placed in clamps cooled in liquid nitrogen. The de-identified frozen samples will be stored at -80°C in the Barshop Institute. Participants will be instructed to refrain from vigorous physical activity and to document their food intake during the 2 days before the biopsy and to repeat this diet before the post intervention biopsy. This procedure will not be performed if IV access cannot be

obtained, if the patient is anticoagulated for any reason and primary care physician does not feel it is safe for anticoagulant to be ceased for 1 week prior to the biopsy, if the patient does not tolerate a prior biopsy, or for any other concern as determined by the PI.

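### The 8-week comparison in Section 12.4 would usually be more precise as an ANCOVA on the baseline value already collected (an improvement, not an error)

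*Combined protocol and SAP*

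**What the plan says.** Section 12.4 specifies two independent-samples t-tests per outcome, one for the acute change over the 400 m walk and "one to compare change before and after chronic (8-week) exercise training between the two groups". No covariate is named; the word 'unadjusted' there refers to multiple comparisons. The only alternative discussed is a mixed-model or repeated-measures ANOVA, which is declined: "The repeated measures ANOVA would be testing more effects than we are exploring here, and the study is not powered for this advanced analysis". ANCOVA is neither mentioned nor ruled out.

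The baseline data are part of the design:

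- Section 5.3 places baseline measurement ahead of allocation: "Phase 2 involves baseline testing. Volunteers then will be randomly assigned to exercise plus placebo".
- Section 7, Baseline Research Testing (Phase 2): "Data for primary and secondary outcomes will be collected using standardized protocols and trained staff".
- Section 7, Post Intervention Testing (Phase 5): "Participants will repeat tests outlined in Phase 2 and the submaximal exercise test outlined in Phase 3".
- Section 8.4 has participants "repeat this diet before the post intervention biopsy", so muscle is sampled at both times.
- Section 7, Randomization (Phase 3), describes a fasting sample at the walk test. It is taken after allocation, "After randomization, vital signs and blood will be drawn before (following a 12 hour fast"), but before the first dose: "After the fasting blood draw, participants will receive (blinded) either" BCAA or maltodextrin.

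Section 12.2 names the estimation of effect sizes for later trials as an important aim.

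**The concern.** A t-test on change is an ANCOVA whose baseline slope is fixed at 1. When the true slope differs from 1, the change score carries avoidable noise. Allocation is randomised, so both analyses estimate the same difference without bias, and the choice affects precision only. In a 24-completer trial meant to supply effect sizes for future work, the width of the confidence interval is a main product of the study.

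The stated case against repeated-measures ANOVA does not carry over. ANCOVA tests one group contrast, as the t-test does, and takes the error degrees of freedom from 22 to 21. Lower sensitivity to chance baseline imbalance is this same gain in precision, not an additional benefit.

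**Working it through.** **Inputs.** From Section 12.2: difference 0.25 µmol/L, SD 0.25 µmol/L, 12 completers per arm, alpha 5%. From Section 12.4: two-sided tests. Assumed, because the documents do not say: 0.25 is the SD of change (the other reading is given below); rho is shown from 0.3 to 0.95; k = post SD / pre SD is shown from 0.9 to 1.25.

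**The plan's own figure.** Normal approximation: n = 2 × (1.960 + 0.842)² × (0.25/0.25)² = 15.7, so 16 per arm; with the t distribution, 17. The stated 12 is not reproduced under a two-sided test. At 12 per arm the standard error is 0.25 × √(2/12) = 0.102, the noncentrality is 0.25/0.102 = 2.45, and with 22 df (critical value 2.074) power is 64.9%. That is the change-score reference.

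**Variance formulas.** With pre SD s and post SD ks:

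- change score: s²(1 + k² − 2ρk)
- ANCOVA residual: k²s²(1 − ρ²)
- first minus second: s²(1 − ρk)², which is never negative

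With k = 1 the ratio of ANCOVA to change variance is (1 + ρ)/2.

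**Cost of estimating the slope.** Chance baseline imbalance inflates the variance by 1 + 1/(N − 4) = 1 + 1/20 = 1.05 on average, and the error df is 21.

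**Worked case, rho 0.5, k = 1.** Residual SD = 0.25 × √0.75 = 0.2165. Standard error = 0.2165 × √(2/12 × 1.05) = 0.0906. Noncentrality = 2.76, critical value 2.080, power 75%.

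**Equal SDs (k = 1), averaged over chance imbalance:**

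| rho | ANCOVA power | CI width, ANCOVA / change | Change-score n per arm with the same power |
|---|---|---|---|
| 0.3 | 80.7% | 0.83 | 17.0 |
| 0.5 | 75.0% | 0.89 | 14.9 |
| 0.7 | 69.7% | 0.95 | 13.3 |
| 0.8 | 67.2% | 0.97 | 12.6 |
| 0.9 | 64.9% | 1.00 | about 12 |
| 0.95 | 63.8% | 1.01 | – |

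**Unequal SDs, ANCOVA power at rho 0.3 / 0.5 / 0.7 / 0.8** (change score 64.9% throughout):

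- post SD 10% smaller: 85 / 80 / 75 / 73%
- post SD 10% larger: 77 / 71 / 66 / 64%
- post SD 25% larger: 73 / 68 / 64 / 63%

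**Where ANCOVA loses.** With equal SDs, above rho of about 0.90. With the post SD 10% larger, between about 0.76 and 0.97; with it 25% larger, between about 0.62 and 0.90. With the post SD 10% smaller, nowhere from 0.1 to 0.99. The worst case is ρk = 1, where the residual variance equals the change variance and only the cost of the extra parameter remains: power 62.7% (64.9 − 62.7 = 2.2 points) and an interval about 2.7% wider.

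**If 0.25 is the SD of a single measurement (k = 1).** Change score against ANCOVA: 51 vs 67%, 65 vs 75%, 86 vs 89% and 96 vs 97% at rho 0.3, 0.5, 0.7 and 0.8; both are 99.9% at 0.9.

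**Simulation.** With 50,000 trials per setting over k = 1, 1.1 and 1.25, both estimators averaged 0.249 to 0.251. Type I error was 0.047 to 0.051 for ANCOVA and 0.048 to 0.051 for the change score.

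**Which baseline.** Phase 2 values precede allocation. For plasma markers, the only fasting draw tied to outcomes in Section 7 is the Phase 3 one. It follows allocation but precedes the first dose, so treatment cannot have altered it and it is a legitimate covariate. The Schedule of Activities is not among the documents, so a separate Phase 2 plasma sample can be neither confirmed nor excluded.

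**The case against.** The planned test is valid, nothing in Section 12 contradicts itself on this point, and the authors chose the simplest comparison on purpose. The gain rests on rho and the SD ratio, and the documents give neither. The largest gains need a low correlation or a shrinking SD, which nothing in the documents supports. 'Usually' describes an average: in simulated trials with equal SDs, the realised ANCOVA interval was wider than the change-score interval in about 6%, 15%, 31%, 44% and 60% of trials at rho 0.3, 0.5, 0.7, 0.8 and 0.9. The figures cover kynurenine only, while the proposal covers every outcome.

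All of this is fair and limits the claim. At rho 0.8 the average narrowing is only about 3%. What decides the matter is asymmetry: the loss is capped at 2.2 points of power, whereas the gain reaches about 16 points at rho 0.3 with equal SDs. Section 12.4 applies one rule to self-reported, performance, blood and muscle outcomes, whose correlations will probably differ. Estimating the slope for each outcome is safer than setting it to 1 for all of them.

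**Conclusion.** The point holds as a recommended improvement, not a correction. ANCOVA estimates the same 8-week difference from data already planned. For kynurenine, with equal SDs and 0.25 read as the SD of change, it narrows the confidence interval by about 17%, 11%, 5% and 3% at rho 0.3, 0.5, 0.7 and 0.8. That equals about 5, 3, 1.3 and 0.6 extra completers per arm. It gives nothing at 0.9 and loses about 1% at 0.95. These sizes depend on the assumed rho and SD ratio. ANCOVA does not repair Section 12.2: it reaches 80% power only at rho of about 0.33 or lower, and the shortfall of 12 per arm is a separate matter.

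**What to change.** In Section 12.4, for the 8-week comparison only, state that each outcome's week-8 value will be regressed on randomised group and that outcome's baseline value, and that the adjusted group difference will be reported with its 95% confidence interval. Define baseline as the Phase 2 value. For plasma markers measured only at the walk test, use the Phase 3 fasting pre-dose sample as baseline and the matching Phase 5 fasting sample as outcome. Keep the unadjusted change-score t-test as a sensitivity analysis. Make the change before unblinding, so that the choice cannot be driven by the results.

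The cost is SAP wording: no new visit, sample or hypothesis. The statistical price is one degree of freedom and about 5% average variance inflation, which gives the small, bounded loss shown above when the true slope on baseline is close to 1.

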This study will address two significant objectives that are critical to aging adults. First, we will examine whether the addition of BCAA to acute and chronic exercise has the ability to reduce mental and physical fatigue. The identification of BCAA added to exercise as superior to exercise alone could have clinical implications for older adults to improve cardiometabolic and functional risk. By reducing fatigue, older adults may be able to engage in longer periods of physical activity, thereby reducing weight gain common to older adults and improving mental and physical quality of life. This study also will address an innovative mechanistic question. This study will begin to fill a knowledge gap by determining whether changes in tryptophan metabolism occur following exercise with and without BCAA supplementation and relate to reductions in mental and physical fatigue as this may identify potential targets for future (lifestyle and pharmacologic) investigation.	Depending on which group a subject is randomized to: 1) Completion of 8 weeks of EX+BCAA 2) Completion of 8 weeks of EX+PLA (placebo) We hypothesize that 8 weeks of EX+BCAA will 1) reduce mental and physical fatigue and 2) increase PGC-1 α , KATs, and kynurenic acid and decrease oxidative kynurenines compared to EX+PLA.	Justification for endpoint comes from the data generated in the past two decades that have shown the advantageous effects of branched-chain amino acids (BCAAs) on exercise performance. Further, studies in animal models suggest that BCAAs decrease the transport of tryptophan and its metabolites into the CNS because BCAAs and tryptophan compete for the same carrier system. Thus, combining BCAA with exercise may synergize to divert metabolism away from formation of neurotoxic tryptophan metabolites with known deleterious effects on mental and physical fatigue.

4. Rationale

Briefly state the reason for conducting the clinical trial.

The rationale of this study comes from the data generated in the past two decades that have shown the advantageous effects of branched-chain amino acids (BCAAs) on exercise performance. Further, studies in animal models suggest that BCAAs decrease the transport of tryptophan and its metabolites into the CNS because BCAAs and tryptophan compete for the same carrier system.

5. Study Design: Double blind Randomized Controlled Trial

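### Section 12.4 makes two whole domains primary and tests each measure at an unadjusted 5%, but no section names the primary measure or the result that counts as success

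*Combined protocol and SAP*

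**What the plan says.** **Analysis (12.4).** The plan states that "two separate independent sample t-tests will be used for each outcome measure": one for change across the 400 m walk, one for change over 8 weeks of training. It then says "This will determine the significance of our primary outcomes (fatigue and tryptophan metabolism) change over time", and "All statistical tests will be 2-sided and unadjusted for multiple comparisons". It declines a mixed-model analysis, partly because "The repeated measures ANOVA would be testing more effects than we are exploring here".

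**Objectives and endpoints (3.1, 3.2).** The objective covers both time frames: "First, we will examine whether the addition of BCAA to acute and chronic exercise has the ability to reduce mental and physical fatigue". The endpoint cell lists completion of 8 weeks in each arm, which is not a measured outcome. A hypothesis follows: "We hypothesize that 8 weeks of EX+BCAA will 1) reduce mental and physical fatigue", and also change PGC-1α, KATs, kynurenic acid and oxidative kynurenines. No instrument or score is named for fatigue.

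**Hypotheses (12.1).** One mechanistic sentence leads with KAT expression and runs through kynurenic acid to fatigue.

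**Sample size (12.2).** The calculation uses kynurenine concentration and claims at least 80% power at the 5% level with 12 per group. The same section calls effect-size estimation an important goal.

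**Procedures (7 and 8.6).** Section 7 (Phase 2) mentions primary and secondary outcomes without sorting them. Section 8.6 lists the FAS, PROMIS-57 and a series of physical-fatigue tests, none marked primary.

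**The concern.** A 5% test protects a conclusion only if the reader knows in advance which test carries it. Here the primary outcomes are two domains, each containing several measures, and the sections that might narrow them point in different directions: completion and a list of outcomes in 3.2, KATs in 12.1, kynurenine in 12.2. Nothing says whether the trial succeeds on any significant result, on one in each domain, or on one particular measure.

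These rules carry very different error rates, and the plan allows the choice to be made once the results are known. A positive headline from a trial with 24 completers could then rest on whichever measure happened to cross 5%. Later studies would be planned on that signal.

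**Working it through.** **1. The plan's own figure (12.2).** Inputs: difference 0.25 µmol/L, SD 0.25 µmol/L, 5% level, 12 per group (12.2); two-sided independent-sample t-test (12.4).

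- Standardised difference: d = 0.25/0.25 = 1.0.
- Normal formula for 80% power: n = 2(1.960 + 0.842)²/d² = 15.7, so 16 per group. The exact t calculation gives 16.7, so 17.
- Power at 12 per group: noncentrality = d√(12/2) = 2.45. The normal approximation gives 68.8% and the exact t-test (22 degrees of freedom) 64.9%.
- Power at 15 per group, with no dropout at all: 75.3%.
- Variants: a one-sided 5% test gives 76.7% at 12 per group. An SD of 0.19 (the spread quoted in 12.2 for the earlier training study) gives 86.9%, but 12.2 assumes 0.25 and 12.4 says two-sided.

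The stated 12 per group for 80% power is not reproduced. The dropout step is: 24/0.8 = 30.

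**2. Error rate under different success rules.** The plan gives no figure to reproduce. Assumptions: 12 against 12, no true effect, two-sided 5% t-tests, equal correlation between measures. If k tests are independent, the chance of at least one false positive is 1 − 0.95^k:

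- k = 2: 1 − 0.95² = 9.75%
- k = 3: 1 − 0.95³ = 14.3%
- k = 10: 1 − 0.95¹⁰ = 40.1%
- k = 11: 1 − 0.95¹¹ = 43.1%

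Correlated cases were simulated:

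| Success rule | Independent | Correlation 0.7 | Correlation 0.9 |
|---|---|---|---|
| Either of 2 tests (one measure per domain, 8 weeks) | 10% | 8.5% | 7% |
| Any of 3 (adding one acute blood measure) | 14% | 11% | 8% |
| Any of 10-11 physical-fatigue readouts, 8 weeks | 40-43% | 22-23% | 13-14% |
| One pre-named measure in each domain, both significant | 0.3% | 1.6% | 3% |
| At least one of 11 in one domain and one of 4 in the other | 8.0% | 9.9% | 8.4% |

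Independence check on the last row: (1 − 0.95¹¹)(1 − 0.95⁴) = 0.431 × 0.186 = 8.0%.

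**3. Where the counts come from.**

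- The three-test row has one acute test because section 7 (Phase 3) describes only vital signs, blood, heart rate and perceived exertion around the walk.
- The 11 readouts are this review's count from 8.6(d): grip in two hands, 1-RM for two lifts, repetitions at 60% 1-RM for two lifts, two chair-rise measures, VO2peak, ventilatory threshold and six-minute distance. Other groupings give 10.
- The 4 are the pathway marker groups in 3.2.

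**The case against.** The strongest defence is that this is a small study that openly declares no adjustment, gives effect-size estimation as an important goal and speaks of exploring effects. For an exploratory trial that is acceptable, and non-adjustment is not in itself the fault. But the plan never calls the trial exploratory. It calls outcomes primary, says the tests will determine their significance, and claims 80% power at 5%. Those claims need a named measure behind them.

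Four stronger readings are tempting, and the documents do not support them:

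- **Every measure is tested twice.** 12.4 says so literally. Section 7, however, describes no fatigue questionnaire, strength test or biopsy before and after the walk. A four-test family with an acute fatigue scale is therefore not supported by the procedures.
- **All the physical-fatigue readouts are primary tests.** Section 8.6(d) lists procedures and does not say that each readout is tested as primary. That row shows how far the wording could stretch.
- **Requiring success in both domains keeps the error below 5%.** That holds with one pre-named measure per domain. If any measure in each domain may count, the rate is about 8-10%.
- **The unblinded statistician will choose the outcome.** Section 5.3 says "Only study team member without direct participant interaction (i.e., statistician) will know supplement allocation", but no section says that this person selects outcomes or runs the tests.

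The attached Schedule of Activities and Form M were not among the text supplied, so the finding covers that text only.

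**Conclusion.** The concern holds in this form: as written, the plan does not determine the false-positive rate of its main conclusion, because it fixes neither the primary measure nor the success rule. Depending on the rule, the rate runs from about 0.3% to 43% in the cases examined. Even the smallest any-significant case, two tests, stays above 5% at correlation 0.9. The absence of a ranking and of a rule is read directly from the text; the rates rest on assumed test counts, rules and correlations.

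The power shortfall in 12.2 (about 65% against at least 80%) is a separate error, and the main point does not depend on it. The data would remain usable, so this should be corrected, but it does not undermine the trial.

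**What to change.** **Main change.** In 3.2, 12.1 and 12.4, before any comparison by arm:

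- The investigators name one primary measure at 8 weeks, for example a specified fatigue scale or a specified kynurenine-pathway measure. Alternatively, they name one per domain in a fixed sequence, each at two-sided 5%, the second tested only if the first is significant.
- State that this alone decides success.
- Report all other measures and all acute comparisons as exploratory between-arm estimates with 95% confidence intervals and no significance claims.

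**Lighter alternative.** Declare the whole trial exploratory and remove the significance and power claims.

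**Separately, in 12.2.** Restate the power for the kynurenine inputs as about 65% at 12 completers per arm, note that 17 per arm would be needed for 80%, and attach the power statement to whichever measure is designated.

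**Cost.** Wording only, with no new visits or data. Fewer results can be called significant, the investigators must rank the two domains, a second test in a sequence is reached only if the first succeeds, and the stated power is less favourable.
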